## **BoneFit: A Student-Led Multimodal Prehabilitation Service for Orthopaedic Surgical Patients in Hull**

### **Introduction:**

In the UK, there are >8 million surgical operations performed every year, and this is likely to continue to rise due to the increasing ageing population [1,2]. Surgery can lead to reduction in physical function, a loss of independence due to continued bed rest and deconditioning, increased pain and discomfort, and can lead to physical and mental complications including increased stress, anxiety and depression. These symptoms can lead to higher readmission rates and longer hospital stays [3].

Due to the recent global pandemic, surgical procedures were cancelled *en masse* leading to increasing waiting lists and, at an individual level, continued deconditioning and an increasing risk of functional limitations particularly in the elderly. In the UK, prehabilitation is a single component of Early Recovery After Surgery (ERAS), a multi-step treatment package designed to help prepare individuals for the physical and mental insult of surgery. Being able to optimise an individual prior to surgery is likely to lead to improved patient outcomes and should save the NHS money by reducing the length of hospital stay, complications and readmission rates [4]. Prehabilitation interventions have evolved over the years becoming multimodal in nature. Interventions typically include exercise, nutrition, and psychological support delivered by a multidisciplinary team [5].

In people receiving orthopaedic surgery, the evidence-base showing the positive impact of prehabilitation continues to grow. In 2023, a large-scale systematic review and meta-analysis based on 48 unique trials involving 3,570 participants (61.5% female, mean age 64 years) reported level I moderate-certainty evidence

supporting prehabilitation versus usual-care for improving pre-operative function and strength in people undergoing total knee replacement (TKR) surgery, and moderate-certainty evidence for increased health-related quality of life (HRQoL) and muscle strength for individuals undergoing total hip replacement (THR) surgery [6].

**Aims:** The aim of BoneFit is to provide local people living in the Hull region with a needs-based prehabilitation care package (PCP) to improve their physical and mental health, quality of life & reduce their length of hospital stay, complications and readmission rates to hospital following orthopaedic surgery (initially TKR and THR procedures).

Currently, Hull University Teaching Hospitals (HUTH) do not offer a prehabilitation/ERAS service for local patients. The University of Hull (UoH) will partner with HUTH to provide a student-led multimodal prehabilitation service for referred patients awaiting orthopaedic surgery (initially TKR or THR). This is a proof-of-concept trial where external funding will be applied for to underpin and expand the service to support other specialities, if shown to be successful.

Only low-to-moderate risk patients will be initially referred to receive a PCP (risk score between 0 to 6). Patients who score  $\geq 7$  points on the operative risk estimation chart will not be referred (see final page of the GP referral form for full details of risk criteria).

### **Study Start and End-dates**

The study is planned to run from March/April 2024 to July 2027. We plan to recruit 50 patients and controls (25 per group). Once these numbers have been achieved we will cease recruitment and just continue with the follow-up visits (final follow up is 12 months following surgery).

- **Inclusion criteria:**

Age 18-75 years;

Waiting for unilateral TKR or THR surgery for a minimum of 6 months;

Able to provide informed consent;

- **Exclusion criteria:**

Previous TKR/THR surgery;

Any medical conditions for which moderate to vigorous exercise is contraindicated;

Patellar or hip joint instability;

Any other disease/condition which severely effects functional performance e.g. stroke or Parkinson's disease;

Age <18 years or >75 years;

No access to smartphone or home internet;

Chronic depression or significant psychiatric disorder;

Enrolled in a clinical trial (or recently completed one);

Cognitive impairment which would affect compliance to BoneFit service;

Patients unable or unwilling to commit to required study follow-ups and unwillingness to work with students;

Pregnancy;

- **UoH Student-Led PCPs:**

All students will work under the guidance of a qualified professional based at the UoH. Multimodal prehabilitation involves the core disciplines of exercise, nutrition and clinical psychology. Therefore, students involved in the following programmes will help supply PCPs as part of their student placements, projects/dissertations or as part of an internship:

- BSc Physiotherapy
- BSc Sports Rehabilitation
- MSc Dietetics
- BSc Sports Nutrition
- MSc Clinical Exercise Physiology
- MSc Cardiovascular Rehabilitation
- Clinical Psychology Doctorate

- **Service Design:**

Following guidance from the 2019 NHS Long Term Plan (<https://www.longtermplan.nhs.uk/>) we will use a personalised approach when developing the PCPs. Validated screening and assessment tools will enable assignment of participants. Those with no increased risk factors and with no increased surgical risk will receive **universal support**. Further assessment will be undertaken for those requiring more than universal support and they will be allocated to **targeted** (intermediate risk/needs) or **specialist** (high risk/complex needs). Patients may receive different levels of support for the different intervention components: exercise, nutrition and psychological support.

**Controls (usual care):** In a non-randomised manner, we will identify a group of age- and sex-matched individuals referred for hip (THR) or knee replacement (TKR) surgery from patients who contact the BoneFit service. PIS forms will be circulated by clinical staff to eligible patients awaiting TKR/THR surgery in their routine clinic at Castle Hill Hospital. Interested parties will contact the BoneFit service for more information. If patients agree to participate they will be invited to the University of Hull to provide consent and will undertake a series of baseline assessments and will be allocated by BoneFit staff to the intervention or control group at this point.

Current HUTH waiting list times for orthopaedic surgery is <18 months. Following referral, patients will be asked to complete DASI, download the (enhanced recovery after surgery (ERAS+) app onto their smartphones and follow its guidance. If they do not have access to a smartphone, they will be referred to the ERAS+ website, or if they have no internet connection, hard copies of generic guidance will be posted to them. At the 2-month point prior to surgery, they will be referred to the Hip-Hub for further evaluation and to receive their PCPs.

The Hip-Hub (<https://hiphub.hull.ac.uk/>)- the UoH sports injuries clinic will manage the patient referral process and BoneFit will benefit from existing referral, data management, facilities, equipment, and communication systems. Referred patients will initially be contacted by Hip-Hub staff and invited to attend for an initial screening session (see Screening, Assessment and Outcomes sections below). Validated screening tools and outcome measures will be used to determine the type of PCP required, and patient data will be recorded. The type of intervention received will depend on whether a patient requires universal, targeted or specialist PCPs. Students will stay in regular contact with patients to ascertain fidelity and compliance with the PCP.

All students will be working under the support and guidance of trained clinical professionals in physiotherapy, sports therapy, nutrition/dietetics, and clinical psychology or clinical exercise physiology. Student-patient interactions will be delivered either in a face-to-face individual or group setting, virtual (one-to-one or group-based using Teams or equivalent) or via telephone. Sessions will mainly be delivered live although some pre-recorded material will be used to supplement live sessions and an online resources library will be built up over time.

Outcome measures for each of the three core components (exercise, nutrition and clinical psychology) will be evaluated at 5 timepoints (initial surgical referral e.g. 18 months from surgery; baseline [2 months from surgery], immediately prior to surgery [2 to 10 days], and 3 and 12 months after surgery). See Table 1 to identify which outcome measures will be recorded. At initial surgical referral, DASI will be completed remotely. However, the remaining 4 timepoints will require face-to-face interactions and more in-depth investigations.

**Table 1.** Outcome and timepoints assessments for individuals recruited to BoneFit

Variable/ Timepoint	2 months from surgery	2-10 days prior to surgery	3 months post op	12 months post op
Physical/ Exercise				
DASI	✓		✓	✓
ISWT	✓	✓	✓	✓
Timed up and go	✓	✓	✓	✓
Hand-grip strength	✓	✓	✓	✓
HOOS-12 or KOOS-12	✓	✓	✓	✓
Nutrition				
MUST	✓	✓	✓	✓
PG-SGA	✓	✓	✓	✓
Clinical Psychology				
EQ-5D-5L (QoL)	✓	✓	✓	✓

GAD-7	✓	✓	✓	✓
PHQ-9	✓	✓	✓	✓
Emotions thermometer	✓	✓	✓	✓
Clinical outcomes				
Length of hospital stay			✓	✓
Complications			✓	✓
Re-admission rates			✓	✓
VAS pain scale	✓	✓	✓	✓

DASI - Duke Activity Score Index; ISWT: incremental shuttle walk test; VAS: visual analogue scale; MUST: malnutrition universal screening tool; PG-SGA: patient-generated global assessment; GAD-7: generalised anxiety disorder assessment; PHQ-9: depression test score; EQ-5D-5L: health and quality of life questionnaire; HOOS-12: hip disability and osteoarthritis outcome score-12; KOOS-12: knee injury and osteoarthritis outcome score-12.

At initial surgical referral, all participants referred for BoneFit will receive existing ERAS guidance on developing healthier lifestyle choices in preparation for surgery

(material delivered by post, or via app and website). It is important to intervene immediately after surgical referral as the longer people sit on a waiting list, the more deconditioned they become, and the harder it is to start making positive life-style choices (low activators). Low mood can increase whilst waiting which can often exacerbate poor lifestyle choices e.g. increase tobacco use, poorer eating habits, wait gain, etc.

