## **Study Outcomes:**

- Primary objective**

The primary outcome measures are feasibility and acceptability of the BoneFit intervention. Feasibility will be assessed by determining the number of participants recruited, trained and retained at the end of the intervention, the proportion of intervention sessions delivered and fidelity of delivery. Moreover, participant recruitment, retention and adherence to the intervention will be measured, as well as any adverse events. To determine the acceptability of the intervention and to explore barriers and enablers to the implementation of the intervention, interviews will be conducted amongst participants (n=6), and staff involved in referral and intervention delivery (n=6) (see process evaluation below).

- Secondary objectives**

- To identify a signal of efficacy for positive changes in physical health (exercise and nutrition), mental wellbeing, and quality of life (using tools described below) compared to usual care;
- To identify differences in DASI, length of hospital stay, complications and readmission rates to hospital following orthopaedic surgery (initially TKR and THR procedures) compared to usual care;
- Assess surgeons' and surgical practitioners' willingness to refer to BoneFit;
- Assess participants experiences of the BoneFit intervention;

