### **Sample Size and Process Evaluation:**

Feasibility studies are typically unpowered, based on similar studies, we will aim to recruit 25 participants to the BoneFit intervention and 25 usual-care controls (n=50).

A concurrent mixed methods process evaluation will explore safety, implementation, delivery, and acceptability of the intervention. We will use semi-structured interviews with participants and practitioners along with process data to assess:

- Barriers to recruitment;
- Acceptability and adherence to the intervention (dose received);
- Intervention delivery (fidelity);
- How the intervention was embedded into clinical practice;
- Safety outcomes: will include adverse events and serious adverse events;
- We will collect quantitative process data on safety, screening and recruitment, fidelity and dose/drop-out which will enable discussions with clinical teams to identify remedial actions to improve recruitment, retention, and fidelity.

We will conduct a pilot feasibility study of the BoneFit intervention which will take approximately 3 years to complete (including all 12-month follow up visits).

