Nutrition	
Dietary advice including basic principles. Supported by regular phone calls / video calls with student nutritionists.
	
Dietetic/nutrition counselling/advice with a student dietitian, including dietary modification, management of nutrition impact factors and oral nutritional supplements. This will be in addition to food fortification advice as per best clinical practice.
	
Artificial nutrition support recommended by a dietitian as per best clinical practice. EXCLUDED FROM INTERVENTION.

------------------	--	--	--

Psychological Support	Signposting to psychological support resources (such as relaxation and mindfulness apps) or as printed resources as appropriate. Supported by regular student-led phone/ video calls	Facilitated peer-group support emphasising mutual problem solving, plus a package of up to 6 1:1 sessions with a student clinical psychologist focusing on self-regulation of stress/anxiety, self compassion and self-soothing skills personalised to individual needs. This is consistent with typical level 2 psychological support practice as per NICE Guidance[64].	Full clinical psychological assessment and individualised intervention plan with a clinical psychologist (or equivalent), as per best clinical practice and Level 3/4 of NICE guidance [64]. EXCLUDED FROM INTERVENTION
------------------------------	--	---	---

If an individual is identified as being in the Specialist group for Nutrition or Psychological Support they would be re-referred via HUTH for specialist care through usu-

al professional service channels. Nutrition/dietetics/clinical psychology students would not be involved in their future care/treatment.

- **Theoretical/Conceptual Framework:**

To maximise patient engagement and adherence a person-centred approach to behaviour change support will be employed across all components (exercise, nutrition and psychological support) [15]. Students will be encouraged to use a motivational-type interviewing, and adopt the COM-B model of behaviour change [16]. We will focus on enhancing participants' self-efficacy (confidence) to engage in new behaviours as well as developing strategies and action plans that meet their priorities and personal circumstances. Approaches will be individualised depending on the level of patient autonomy required to adhere to the PCPs.

- **Anticipated impact:**

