BoneFit will benefit the NHS and patients in 4 ways: 1) informing clinical guidelines and developing the evidence-base around multimodal prehabilitation for patients requiring orthopaedic surgery; 2) improving local patient care and service delivery through enhancing equity of access to services and building on the principles required to deliver effective, safe services. Supporting patients who would benefit from optimisation of co-morbidities and needs-based multimodal PCPs, thereby helping them "wait well" for surgery; 3) identifying and delivering education, training and advocacy for student healthcare professionals; 4) local workforce transformation through informing the development of new service pathways. Further funding from national (NIHR, MRC, orthopaedic charities) and local/regional sources will be sought if we can identify that the pathway is successful in terms of improving patient outcomes.

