#### Identification of participants:

Participants awaiting TKR/THR surgery will be provided with PIS V4 regarding BoneFit during routine clinics at Castle Hill hospital. Contact details of the BoneFit team are included and interested parties are encouraged to contact the team. Interested

parties will be invited to the University of Hull for consenting, baseline assessments, and allocation to the intervention or control groups. Hull University Teaching Hospitals Trust staff are only required to bring the trial to the attention of suitable patients at routine THR and TKR clinics and direct them to the participant information sheets. Interested parties should then contact the BoneFit team.

Arrangements for the collection, use, sharing, security and integrity of participant data:

The BoneFit team at the University of Hull may require limited patient data from NHS organisations including Hull University Teaching Hospitals Trust. All data requested will be anonymised and each patient will receive a unique identification code. The University will only request data that is pertinent to the BoneFit intervention. For example, details of psychological interventions undertaken as a consequence of BoneFit screening into universal, targeted or specialist groups. Information requested for targeted interventions would include number of sessions undertaken, intervention details, and intervention outcomes following initial screening. NHS organisation could provide this information in the form of a brief summary statement and there is certainly no requirement for University staff to receive patient notes. This has been discussed with the Clinical Psychology team at HUTHT.

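### Service staff allocate patients to arms non-randomly after baseline, with age and sex matching the only stated constraint, so the secondary comparisons with usual care are open to selection bias

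*Protocol*

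**What the plan says.** The Controls (usual care) paragraph of the protocol sets out how the groups are formed: "In a non-randomised manner, we will identify a group of age- and sex-matched individuals" from those who contact the service. After consent at the University, patients "will undertake a series of baseline assessments and will be allocated by BoneFit staff to the intervention or control group at this point". The section on identification of participants gives the same order: interested "parties will be invited to the University of Hull for consenting, baseline assessments, and allocation to the intervention or control groups". No sequence, decision rule, concealment or independent allocator is described, and no matching factor other than age and sex is named.

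Under Study Outcomes, feasibility and acceptability are primary. The secondary objectives compare the arms. One is "To identify a signal of efficacy for positive changes in physical health", mental wellbeing and quality of life against usual care. Another looks for differences in DASI, length of stay, complications and readmissions against usual care. The sample size section plans 25 per arm and notes that "Feasibility studies are typically unpowered". Under Anticipated impact, further funding "will be sought if we can identify that the pathway is successful in terms of improving patient outcomes".

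**The concern.** The people who run the service choose each patient's arm after meeting the patient and at a point when baseline results exist. Age and sex matching leaves everything else free: joint, function, mood, pain, surgical risk, motivation and likely adherence. If staff tend to place fitter or keener patients in the programme, the intervention arm will look better without any treatment effect. If they tend to place needier patients there, a real benefit can be hidden.

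This affects only the secondary comparisons. They still carry weight, because the protocol ties its case for further funding to improved patient outcomes and attaches no caveat about how the arms were formed. Allocation is also fixed by the protocol: an analysis plan can adjust for measured differences but cannot make the allocation random.

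**Working it through.** **What the protocol fixes.** Sample size: 25 + 25 = 50, as stated. It gives no power calculation, SD, effect size or dropout rate, so there is no further figure to reproduce.

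**Precision.** In units of the outcome SD, with all 50 patients analysed, the standard error of a mean difference is sqrt(1/25 + 1/25) = sqrt(0.08) = 0.283.

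**Bias formula.** With no true effect, the spurious difference is (imbalance in a trait, in SD) × (correlation r of that trait with the outcome). For an assumed imbalance of 0.5 SD and r = 0.5, it is 0.5 × 0.5 = 0.25 SD, or 0.25 / 0.283 = 0.88 standard errors. A two-sided 5% test would then reject a true null 14% of the time. Under randomisation the expected imbalance is 0 and the rate stays at 5%.

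**Simulation.** All inputs are assumed; none comes from the protocol. There are 50 patients and no true effect. The chance of receiving the intervention rises with a trait at an odds ratio (OR) of 1.25 to 3 per SD, and r runs from 0.3 to 0.7. Five cases:

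- A: no adjustment.
- B: one of each age- and sex-matched pair is chosen, for a trait unrelated to age and sex; no adjustment.
- C: trait measured without error and adjusted for.
- D: trait measured with reliability 0.7 and adjusted for.
- E: trait unmeasured; the outcome's own baseline is adjusted for (assumed correlation 0.3 with the trait and 0.5 with the outcome).

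Bias in SD at r = 0.5, with the full range over all ORs and r = 0.3 to 0.7 in the last row:

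| OR | A | B | C | D | E |
|---|---|---|---|---|---|
| 1.25 | 0.11 | 0.11 | 0.00 | 0.04 | 0.08 |
| 1.5 | 0.20 | 0.19 | 0.00 | 0.06 | 0.13 |
| 2 | 0.31 | 0.29 | 0.00 | 0.10 | 0.22 |
| 3 | 0.43 | 0.38 | 0.00 | 0.15 | 0.31 |
| Range | 0.07–0.61 | 0.07–0.53 | 0.00 | 0.02–0.21 | 0.03–0.49 |

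A repeat run agreed within about 0.01 SD. With selection reversed at OR 2 and r = 0.5, case A gives −0.30.

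**Reading the table.** Age and sex matching (B against A) barely reduces bias from other traits. Adjustment removes it fully only when the driver of selection is measured without error (C). For an imperfectly measured driver (D) it leaves about a third: 0.10 / 0.31 = 0.32. For an unmeasured driver (E) it leaves about 0.22 / 0.31 = 0.71.

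**The case against.** The design is declared openly. The protocol says the groups are not randomised, calls the trial proof-of-concept, makes feasibility primary and speaks only of a signal of efficacy. All of that stands, and it limits the weight of the point. It does not remove it: low power shows in a wide interval, whereas selection bias does not show in the interval at all.

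Both arms come from the same self-referring pool under the same eligibility criteria, so a contrast between volunteers and non-volunteers is absent. Table 1 collects function, strength, nutrition, mood, quality of life and pain at baseline, and an analysis plan not seen here may adjust for them. That also stands.

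Three stronger readings are tempting, and the protocol does not support them:

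- *The comparisons cannot separate treatment from selection at all.* Case C shows that they can, if the drivers are well measured and adjusted for. The residual concern is traits measured poorly or not at all.
- *Staff select on baseline results.* The protocol nowhere says so. It only fails to prevent it.
- *The Specialist tiers remove the worst-off from the intervention arm only.* Table 2 marks the nutrition and psychology Specialist tiers "EXCLUDED FROM INTERVENTION", and a patient "identified as being in the Specialist group for Nutrition or Psychological Support they would be re-referred via HUTH for specialist care". The text does not say that such patients leave the study or its follow-up. The data section expects details of psychological interventions after screening into any of the three levels. Loss from one arm is therefore not established.

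**Conclusion.** The point holds as a weakness in how patients are allocated, confined to the secondary comparisons with usual care. The primary outcomes are unaffected. Neither the size nor the direction of the bias follows from the protocol. As an illustration, roughly 0.1 to 0.5 SD is possible, set against a standard error of 0.28 SD. It would be smaller where selection is weak or its driver is measured and adjusted for, and zero if staff choices happen to be unrelated to prognosis. These figures rest wholly on the assumed odds ratios, correlations and reliability. Confidence is high on what the protocol says and low on how large the bias would be. It should be fixed because the remedy is cheap at this step and the funding statement would otherwise carry a non-randomised difference forward as improvement.

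**What to change.** **Preferred.** At the existing allocation step, replace staff allocation with concealed 1:1 computer randomisation in permuted blocks stratified by joint (TKR or THR). Hold the list outside the service team and do not disclose the block size to it. State that this replaces age and sex matching. Analyse every patient in the arm assigned, including anyone later found to be in a nutrition or psychology Specialist tier. Report patients already allocated by staff separately from those randomised.

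Do not add a tier assessment of all patients before randomisation. The nutrition assessment can lead to prescribed supplements and the psychological one is a contact with a student psychologist, so both could expose controls to parts of the intervention.

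**If randomisation is not adopted, or recruitment is complete.** Allocate any remaining patients by a fixed rule that does not depend on baseline results. Amend the secondary objectives and Anticipated impact so that between-group differences are described as non-randomised and exploratory, not as evidence that the pathway improves outcomes.

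**Cost.** A protocol and participant information sheet amendment, a randomisation list and slightly less control over student caseload. With blocks of 4 in two strata totalling 50, the unfilled blocks hold 0 and 2, 1 and 1, or 3 and 3 patients. Each combination gives a difference of at most 2, so the arms are 24:26 at worst. No extra patients are needed, because consent and baseline already come before allocation and the text gives patients no choice of arm.

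The study was planned to start in March/April 2024, and the protocol does not say how many patients are already allocated. If 10 or 20 of the 50 are, the randomised comparison rests on 40 or 30, and its standard error rises from 0.28 to sqrt(4/40) = 0.32 or sqrt(4/30) = 0.37 SD.

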### **Screening and Assessment for Exercise/Fitness/Functional Capacity:**

Screening: We will use the Duke Activity Status Index (DASI) [7] to screen for reduced functional capacity. Patients with a DASI score > 34 are at low risk and will be assigned to **universal support**, those with a DASI score <34 will be referred for an assessment.

Assessment: An incremental shuttle walk test (ISWT)[8] will be performed to assess patients' functional capacity. Patients with ISWT distance of <475m will be assigned to **targeted** intervention. Patients with a ISWT distance of <400m or patients with a medical comorbidity that necessitates supervised exercise will be assigned to **specialist** intervention. If a patient is deemed unsuitable to complete the ISWT by the clinical supervisor due to functional limitations or progressive pain, we will ask them to just undertake a Timed Up and Go test and use this to screen into targeted (<18 seconds), or specialist groups (>=18 seconds).

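### Cheap improvement, lowest severity: DASI is never recorded between prehabilitation and surgery, because Table 1 leaves it out of the 2-10 day visit

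*Protocol*

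**What the plan says.** The text before Table 1 names five timepoints: surgical referral, 2 months before surgery, and "immediately prior to surgery [2 to 10 days], and 3 and 12 months after surgery". DASI is completed remotely at referral, and the other four timepoints are face-to-face. For the content of the visits the text defers to the table: "See Table 1 to identify which outcome measures will be recorded".

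In Table 1 the DASI row is ticked at 2 months before surgery and at 3 and 12 months after it. The cell for 2-10 days before surgery is blank, and no reason is given.

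The paragraphs on controls and referral place the start of the PCP: "At the 2-month point prior to surgery, they will be referred to the Hip-Hub for further evaluation and to receive their PCPs".

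Two secondary objectives under Study Outcomes bear on DASI. The first is "To identify a signal of efficacy for positive changes in physical health (exercise and nutrition), mental wellbeing, and quality of life (using tools described below"); its comparator is usual care. The second is "To identify differences in DASI, length of hospital stay, complications and readmission rates to hospital following orthopaedic surgery", also compared with usual care. The section on exercise screening gives DASI its other role: "We will use the Duke Activity Status Index (DASI) [7] to screen for reduced functional capacity".

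**The concern.** The PCP is delivered before surgery, so its effect on function, separate from that of the operation and recovery, can be seen only in readings taken after the PCP and before the operation. Table 1 takes almost every measure at that point, but not DASI. The first secondary objective looks for change in physical health using the tools described later in the protocol. DASI is one of those tools, and the objective is not confined to the post-operative period.

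What is at stake is one supporting comparison on one instrument. A score that is not collected cannot be reconstructed, so this has to be settled in the schedule and cannot be left to the analysis.

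**Working it through.** **Count of the schedule (Table 1).**

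- Rows in the table: 15.
- Rows that exist only after surgery (length of stay, complications, readmission): 3.
- Measures obtainable before surgery: 15 - 3 = 12. They are DASI, ISWT, Timed Up and Go, hand-grip strength, HOOS-12 or KOOS-12 (one row), MUST, PG-SGA, EQ-5D-5L, GAD-7, PHQ-9, emotions thermometer and VAS pain.
- Ticked at 2 months before surgery: 12 of 12.
- Ticked at 2-10 days before surgery: 11 of 12. The exception is DASI.
- Within the physical/exercise block, 4 of 5 are ticked at 2-10 days.

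**Order of DASI readings relative to the PCP.**

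| DASI reading | Source | Position |
|---|---|---|
| Referral (remote) | Text before Table 1 | Before the PCP |
| 2 months before surgery | Table 1 | Before the PCP (baseline) |
| 2-10 days before surgery | Table 1 | Not scheduled |
| 3 months after surgery | Table 1 | After PCP and surgery |
| 12 months after surgery | Table 1 | After PCP and surgery |

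No pair of readings spans the PCP alone. The referral and 2-month pair spans waiting time before the PCP. Every pair with a later end point also includes the operation and recovery.

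**Volume of the addition.** Table 1 readings of DASI now: 3 x 50 = 150. With the extra cell: 4 x 50 = 200. The difference is 50 questionnaires at full retention, and fewer with dropout.

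**Precision of the added comparison.** The protocol gives no SD, effect size or dropout rate, so the result is in SD units. The inputs are 25 per group (Sample Size and Process Evaluation), a two-sided 95% interval and no loss to follow-up.

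- Unadjusted half-width = t(48 df) x sqrt(2/25) = 2.011 x 0.283 = 0.57 SD.
- Adjusted for baseline DASI, half-width = t(47 df) x sqrt((2/25)(1 - r²)), where r is the correlation between the baseline and later score. The protocol gives no r. An assumed r = 0.5 gives 0.49 SD, and an assumed r = 0.8 gives 0.34 SD.

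The unadjusted figure applies to any complete continuous outcome at this sample size, so it describes the study's size and is not specific to DASI.

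**The case against.** The strongest reply is that the blank is a sound choice about burden. The objective that names DASI lists it with outcomes after surgery, and a 2-month baseline with 3- and 12-month readings is what that objective needs. The first objective does not say that every tool is used at every visit. DASI is introduced as a screening tool. The ISWT assesses functional capacity directly and is taken at 2-10 days with Timed Up and Go, hand-grip strength and HOOS-12/KOOS-12.

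Most of this stands, and it keeps the point at the lowest severity. It does not remove it. The exercise assessment section allows patients judged unsuitable for the ISWT to do only Timed Up and Go, so the most direct functional-capacity measure may be missing for some patients. A questionnaire could still be completed by them.

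Three stronger readings are tempting, and the protocol does not support them.

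- A reader might infer that DASI has no pre-operative data at all. It has two pre-operative readings, at referral and at 2 months. What is missing is one after prehabilitation.
- A reader might infer that Table 1 contradicts the objectives. It does not: the text defers to the table, and the second secondary objective is served by the existing schedule.
- A reader might take the Introduction's evidence, "supporting prehabilitation versus usual-care for improving pre-operative function and strength in people undergoing total knee replacement (TKR) surgery", as a reason why DASI must be measured just before surgery. The Introduction does not say that function was measured by DASI, and other Table 1 tools measure function and strength in that window.

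**Conclusion.** The point holds as an optional, low-cost improvement. DASI is the 1 of 12 pre-operatively obtainable measures without a 2-10 day reading, so it cannot contribute a post-prehabilitation, pre-operative difference from usual care to the first secondary objective. The 3- and 12-month DASI comparisons and the primary outcomes are untouched.

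The gain from closing the gap is limited. The controls are not randomised, and the protocol describes the sample as unpowered: "Feasibility studies are typically unpowered, based on similar studies, we will aim to recruit 25 participants to the BoneFit intervention and 25 usual-care controls". A half-width of about 0.57 SD unadjusted could support only a signal. That figure assumes 25 complete pairs of groups' data, that is, all 50 participants retained to the visit. The adjusted figures rest also on the assumed correlations.

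The count assumes that the blank cell is real and not a tick lost when the table was read from PDF. The alignment of the later ticks in the row supports this.

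**What to change.** In Table 1, tick DASI in the column for 2-10 days before surgery. The baseline, 3-month and 12-month readings stay as they are.

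The cost is a one-cell amendment and one more short questionnaire per patient, at most 50 in all, at a face-to-face visit that already takes place. The downside is slightly more patient burden at that visit. The sample size and the number of visits do not change. The change helps only participants who have not yet passed their pre-operative visit, so it is worth more if made early.

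If the sponsor prefers to keep the blank, a sentence saying that it is intended would spare readers the question. That would only record the present schedule and would not supply the missing comparison.
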